### **Reproductive Risks**

The effects of topical doxycycline on an unborn fetus or nursing (breast feeding) infant are unknown. It is possible that use of NANODOX® hydrogel may be associated with unanticipated risks to a pregnancy or fetus. Women of child bearing potential will be counseled to use acceptable birth control methods. Women will not be allowed to participate in this study if they are pregnant, become pregnant, or are nursing an infant.

### **Property damage risks**

Objects in contact with NANODOX® may have discoloration (e.g. bedding, towels, clothes). Subjects are advised to be careful handling the opened NANODOX® packages and to rinse the excess of product from their skin if they observe change in color to minimize the likelihood of stain on towels, rugs or other clothing.

### **General Risks**

When participating in any research study there is a possibility for invasion of privacy or breach of confidentiality.

### **Adverse Event Reporting**

An adverse event (AE) is any observation whether or not considered to be product related, that is unfavorable and unintended and that occurs after any use of an investigational medicinal product.

Any observation of abnormality will be documented on the Adverse event form. The Investigator will document the date of occurrence, severity, resolution, and will assess the relationship of the adverse event to the study drug by assigning a causality assessment. Results from laboratory evaluations which are outside of the laboratory reference range will constitute an adverse event only if the Investigator determines that the result is clinically significant.

Severity will be assessed by the following system:

- Mild: easily tolerated, causing minimal discomfort
- Moderate: sufficiently discomforting to interfere with every day activities
- Severe: prevents normal every day activities

### **Serious Adverse Events**

FDA definition: A serious adverse event results in death, is life-threatening, requires inpatient hospitalization or prolongation of existing hospitalization, results in persistent or significant disability / incapacity, results in a congenital anomaly / birth defect. Events fitting these descriptions will be considered adverse events if they occur after treatment with the study drug.

As soon as reasonably possible, subjects will contact the Investigator to report any unfavorable events. The Investigator will assess the case, determine the need for treatment, and consult with Alchem Laboratory, Inc, particularly in the occurrence of:

- A serious adverse event.
- An unusual frequency of non-serious adverse events.
- Death, even if this does not appear to be related to therapy with the study drug.

The Investigator will notify the sponsor (Alchem Laboratory, Inc and CTSI) and the UF Institutional Review Board within approximately 3 working days if a serious adverse event occurs.

### **Causality assessments**

#### Probable

All of the following apply:

- Reasonable association in time between the administration of the study drug and onset and duration of the reported event.
- Description of the clinical phenomenon should be consistent with, or at least plausible, given the known pharmacology and toxicology of the product.
- There should be no other equally plausible explanation(s) of the case. In particular, concurrent use of other products (and possible interactions) or concurrent disease should be taken into account in the assessment.

#### Possible

- The causality is one (of other) possible and plausible causes for the described event, but the data do not meet the criteria for inclusion in Category A.

#### Unknown

- An association with the study drug cannot be discounted, but other factors prevent a conclusion from being drawn.

#### Unlikely

- Sufficient information exists to establish beyond reasonable doubt that the product was not likely to be the cause of the event.

### **Classification of adverse events**

At the conclusion of the study, Medicinal Dictionary for Drug Regulatory Authorities (MeDDRA) terms will be assigned to all adverse events and will be included in the final study report.

### **Stopping Criteria**

If more than 5 patients report a greater than moderate local side effect (irritation, worsening of rash, etc) or if the clinical dermatological score in the target lesion area as assessed by the clinician has worsened by more than 50% from baseline in more than 5 patients, then all

patients will stop medication until further review and changes made to the protocol. If any unanticipated serious adverse effects are noted all subjects will be notified and changes will be made to future protocols and submitted for approval.

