### **Inclusion Criteria**

- Male or female, 18 through 65 years of age, inclusive who are generally healthy except for active atopic dermatitis diagnosed by the following criteria.
- **Active Atopic Dermatitis:** Subjects *must have* according to medical records, patient account or by medical exam of the investigator:
  - Pruritus
  - Eczema (acute, subacute, chronic)
  - Chronic or relapsing history

Most subjects *will have* (seen in most cases, adding support to the diagnosis):

- Early age at onset
- Atopy
- Personal and/or family history
- Xerosis

Subjects *may have* (these clinical associations help to suggest the diagnosis of AD but are too nonspecific for defining or detecting AD for research or epidemiological studies):

1. Atypical vascular responses (e.g., facial pallor, white dermographism, delayed blanch response)
  2. Keratosis pilaris/hyperlinear palms/ichthyosis
  3. Ocular/periorbital changes
  4. Other regional findings (e.g., perioral changes/periauricular lesions)
  5. Perifollicular accentuation/lichenification/prurigo lesions
- Moderate to Severe AD: clinical score based on EASI  $\geq$  10 and/or IGA 1-2.
  - If receiving antihistamines, are on a stabilized dose, and expect to maintain this dose throughout the study
  - All female subjects of childbearing potential must have a negative pregnancy test at screening visit and must be on an acceptable methods of contraception from the Screening Visit continuously until 30 days after stopping study drug.

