**Study procedures & methods**

- **Disease status assessment:** **1)** Investigator Global Assessment (IGA), which will provide information of the overall disease (four point scale: clear, mild, moderate, severe) and it is the score requested by FDA for clinical study and **2)** Eczema Area and Severity Index (EASI), a well-accepted and validated scoring system for general disease activityxiv. It is the sum of the intensity scores (0 to 3) for four signs: erythema, induration, excoriation, lichenification and it is recorded for targeted treatment areas as well as four regions of the body (i.e., head, trunk, lower and upper extremities). Data will be reported as percent change in EASI score from baseline and each visit. Proportion of participants achieving EASI50 and EASI75 will be determined at each study timepoints. The presence or absence of skin irritation (e.g. macular/papular eruption), redness, atrophy and telangiectasia will be noted at each study visit.  
**3)** The pruritus intensity will be assessed using the 5-D Pruritus Scale. The pruritus categorical scale is a 4-point scale commonly used in clinical studies of AD and has less of a “middling” effectxv The scale is rated as follows: 0: absence of pruritus; 1: mild, pruritus (occasional slight itching/scratching); 2: moderate pruritus (constant or intermittent itching/scratching that does not disturb sleep) and 3: severe pruritus (bothersome itching/scratching that disturbs sleep).
- **Digital pictures:** A digital picture will be taken with a dedicated digital camera. The pictures will be labeled with the subject’s study ID and date. Pictures will not include identifying information (e.g. facial features, tattoo, etc). Pictures will be taken at a distance for easy identification of the anatomical area and closer to better capture clinical changes. Digital photographs will be used to record the location and monitor the size of target lesions. Quantification of change in size will be obtained using Image J software.  
At conclusion of the study, two trained physicians/dermatologists will be asked to score clinical pictures (0-4 scale, clear, mild, moderate, severe) in a blind fashion (*i.e.*, pictures will be de-identified and presented randomly/ not in chronologic order). This would allow to objectively confirm the clinical score taken during the study.

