### **Risks of NANODOXY® 1% hydrogel**

Subjects may experience local irritation including redness, pain, stinging or burning sensation in the treatment area. Systemic doxycycline can enhance sensibility to the sun light. It is possible that topical application might temporarily enhance risk of sunburn in the treated site. To minimize risk of sunburn we will instruct the subjects to apply the topical at bedtime and rinse off in the morning. In case of sun exposure subjects should use appropriate sun protection (SPF >30 or clothing). Some patients may experience some irritation from the NANODOXY® hydrogel especially in areas of open skin from scratching. Some patients may experience increased dryness from the hydrogel formulation. All patients will be advised to moisturize in the morning and use gentle body wash to minimize these potential side effect.

As for any antibiotic, there might be a risk of inducing antibiotic resistance. To minimize the risk the drug will be used only until the lesion is active/visible. Also we will be monitoring for bacteria growth during the study to determine possible change in bacteria contamination as well as antibiotic resistance.

Preclinical studies have shown that over time (12-24 hours) the color of leftover products in the package might change from a white transparent tone to a more yellow-brown color. Change in color has not been associated with change in efficacy. To minimize risk of skin discoloration we will advise the subjects to rinse off the site in the morning.

Subjects with sensitivity to doxycycline might develop an allergic drug reaction, which could vary from local irritation to more severe systemic reaction. Subjects with sensitivity/allergy to

tetracycline will not be enrolled in the study.

In case of any abnormal reaction we will instruct the subjects to call the dermatology office and stop using NANODOX® until discussing symptoms with study team.

Risks to children or pets are not known and subjects will be instructed to keep the products out of reach from children and pets. Because this is an investigational medication/formulation some side effect may not yet be known. Any adverse reaction will be accounted.

Based on preliminary data, we do not anticipate any complications associated with the use of topical doxycycline.

Common skin reactions with taking oral doxycycline include:

- Redness
- Swelling
- Blistering rash

Common allergic reactions with taking oral doxycycline include:

- Hives

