## **5. DATA ANALYSIS AND DATA MONITORING**

### **Primary Outcomes:**

1. Assessment of safety and tolerability of NanoDOX® Hydrogel in AD subjects on lesional and non-lesional (clinically normal appearing) skin, including pain and dermatologic/skin toxicity (incidence, severity, frequency, duration and causality) in lesional skin at target site (NanoDOX® Hydrogel). 2. Improvements rate of IGA and EASI score in lesional skin treated with NanoDOX® Hydrogel before and after treatment. We will quantify clinical improvement as: IGA (0-4) fold improvement from baseline; percent of subjects reaching EASI50 (50% improvement over baseline) or EASI75 (75% improvement over baseline) at each time point post treatment (V2 and V4). 3. Objective Clinical improvement based on digital photography scoring (0-4 scale and size of active lesion), measured as fold improvement over baseline at each time point (V2 and V4).

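### The stopping rule does not name its score; on the 0–12 target-lesion sign sum, worsening of more than 50% cannot be reached from a baseline of 8 or more

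*Combined protocol and SAP*

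**What the plan says.** The Stopping Criteria in section 4 have two numerical limbs. Either one halts dosing for everyone, pending review and protocol changes.

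- Side-effect limb: "If more than 5 patients report a greater than moderate local side effect (irritation, worsening of rash, etc").
- Score limb: a clinician-rated dermatological score of the target lesion "has worsened by more than 50% from baseline in more than 5 patients".

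The score in the second limb is not identified. Two candidates are described under Study procedures & methods.

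- **EASI sign score.** The protocol defines it in these terms: "It is the sum of the intensity scores (0 to 3) for four signs". On where it applies, the same section states that "it is recorded for targeted treatment areas as well as four regions of the body".
- **IGA.** This is presented as a measure of overall disease on a "four point scale: clear, mild, moderate, severe". The Primary Outcomes section gives a different range: "IGA (0-4) fold improvement from baseline".

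Other uses of the term do not settle the matter. The visit lists ask for a clinical score without naming it. The Inclusion Criteria use the term for either scale: "Moderate to Severe AD: clinical score based on EASI" of at least 10, and/or an IGA of 1–2.

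**The concern.** A numerical pause rule can be applied consistently only if its score is fixed. The choice matters here because a percentage-worsening threshold on a bounded score has a ceiling: the higher a lesion starts, the less room it has to worsen in relative terms. Above some baseline the threshold cannot be met.

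The score limb is the only numerical trigger that rests on the clinician's own rating of the treated skin. Safety and tolerability at the target site is the first primary outcome. If higher-scoring lesions cannot register on this limb, marked deterioration in them would not count toward the score-based pause.

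**Working it through.** **The plan's own figure.** The stopping rule comes with no operating figure. The only one in the plan concerns efficacy: 6 or more responders of 15 at a true rate of 60%, stated as over 96%. The exact binomial gives 0.966, which agrees, but it does not bear on this point.

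**Which score.** The sign sum is the closer textual match, because the protocol says it is recorded for the target area, whereas the IGA is described as an overall rating. The sum has 4 signs × 3 points = 12 as its maximum. This assumes that the target-area version carries no area term, which the protocol does not state either way.

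**Ceiling.** From baseline B on a score with maximum M, the largest possible worsening is (M − B)/B. This exceeds 50% only if B < M/1.5. With M = 12, the limit is B < 8.

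**Points needed.** The current rule needs the smallest whole score above 1.5 × B. The last column adds the alternative of a rise of at least 3 points.

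| Baseline | Largest possible worsening | Score needed now | Rise needed now | Rise needed with 3-point alternative |
|---|---|---|---|---|
| 1 | 1100% | 2 | +1 | +1 |
| 2 | 500% | 4 | +2 | +2 |
| 3 | 300% | 5 | +2 | +2 |
| 4 | 200% | 7 | +3 | +3 |
| 5 | 140% | 8 | +3 | +3 |
| 6 | 100% | 10 | +4 | +3 |
| 7 | 71.4% | 11 | +4 | +3 |
| 8 | 50.0% | 13, not possible | none | +3 |
| 9 | 33.3% | 14, not possible | none | +3 |
| 10 | 20.0% | 16, not possible | none | none (10 + 3 = 13 > 12) |
| 11 | 9.1% | 17, not possible | none | none |
| 12 | 0% | 19, not possible | none | none |

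**The boundary case.** A lesion whose four signs all go from 2 to 3 moves from 8 to 12. That is 4/8 = 50.0%, which is not more than 50%, so it is not counted. The same 4-point rise from 7 to 11 is 4/7 = 57.1% and is counted. Half-point steps do not move the limit: 7.5 × 1.5 = 11.25 can be exceeded, and 8 × 1.5 = 12 cannot.

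**When the limb is fully disabled.** The count must reach 6. With 15 patients, if 10 or more target lesions start at 8 or above, at most 15 − 10 = 5 can be counted and this limb cannot fire. The documents do not say whether that would happen.

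**If the score were the IGA.** With the four grades coded 0–3, a baseline of 2 can worsen by at most (3 − 2)/2 = 50%, so it is blocked. On a 0–4 scale, a baseline of 1 can worsen by 300% and a baseline of 2 by 100%, so neither is blocked. A baseline of 3 can reach only (4 − 3)/3 = 33.3% and is blocked.

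**The case against.** **The other limb already names rash worsening and has no ceiling.** This is true, and a lesion going from 8 to 12 could count there. The overlap is only partial. That limb depends on what patients report and requires an effect beyond moderate. On the severity scale under Adverse Event Reporting, the grade above moderate is severe, which means that ordinary daily activities are prevented. That is a high bar for a treated site the size of an index card.

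**Individual patients are protected in other ways.** For any abnormal reaction, "we will instruct the subjects to call the dermatology office and stop using NANODOX" until the symptoms have been discussed. Flares in the treated area may receive supervised rescue, and the investigator consults the drug supplier if non-serious events are unusually frequent. These safeguards stand and limit the harm, but none is a numerical study-wide pause.

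**The ceiling is conditional.** This also stands. The Stopping Criteria do not cite the sign sum, and a target score with an area term would have a different ceiling. Only the missing name is unconditional.

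**A reader might infer that most lesions are blocked because the trial enrols moderate-to-severe disease.** The documents do not support this. The entry thresholds are general disease scores, no minimum is set for the target lesion, and the site is chosen by location, with arms preferred.

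**A reader might also infer that the IGA reading fails in the same way.** It does so only in part. Entry at IGA 1–2 is not blocked on the 0–4 scale, and the IGA is the weaker candidate for a target-area rule.

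**Conclusion.** The concern holds in a limited form. The score limb does not name its score. On the closest textual match, the 0–12 four-sign sum without an area term, the threshold is unreachable from every baseline of 8 to 12 and reachable from every baseline of 1 to 7. For the affected lesions, only the side-effect limb can contribute to the study-wide pause.

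It would go too far to say that the stopping rule as a whole is inoperative: the side-effect limb is untouched, and lesions starting at 1–7 still count on the score limb. Nor can a loss in the chance of a pause be quantified. The documents give neither a distribution of baseline target-lesion scores nor a rate of worsening, so any firing probability would rest on invented inputs.

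This is a cheap improvement of minor severity. No efficacy estimate or decision depends on it.

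**What to change.** In the Stopping Criteria, name the target-lesion four-sign sum (0–12) as the score. Count a patient as worsened if the sum rises from baseline by more than 50% or by at least 3 points. Keep the count of more than 5 patients. State that lesions starting at 10–12, where a 3-point rise is impossible, rely on the side-effect limb.

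The 3-point margin is a judgement. It equals what the current rule already requires at baselines 4–5. Baselines 1–5 are unchanged, 6–7 need +3 instead of +4, and 8–9 become countable at +3. The uniform change from 2 to 3 on all four signs would then be counted.

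The cost is one reworded paragraph submitted as a protocol amendment. No new data are needed, because the target-area sign scores are already recorded. The downside is a slightly more sensitive pause rule at baselines 6–9. How often that would matter cannot be computed from the documents.

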## 2. CHARACTERISTICS OF THE RESEARCH POPULATION

**Number of subjects** We intend to have 15, non-pregnant, non-lactating women and men of any race and ethnicity, ages 18 to 65 yrs, who are generally healthy except for atopic dermatitis diagnosed by the US Consensus criteria complete this study. This may require enrolling up to 30 subjects depending on retention rates and dropouts. Patients can have other allergic conditions such as asthma, allergic rhinitis, food allergies, etc. All AD subjects must have

moderate-severe AD as defined at screening by an Eczema Area and Severity Score (EASI)  $\geq$  10.

**Gender of subjects** We will be recruiting both male and female subjects

**Age of subjects** We will be including subjects between the ages of 18 and 65 years.

**Racial and Ethnic Origin** We will not have any restrictions based on racial or ethnic origin. We based our target research population racial and ethnic distribution on the data of the 2000 United States Census for the Alachua Area.

**Vulnerable subjects** We will not be targeting vulnerable subjects, however staff and students of UF and Shands may be enrolled as part of the general population with AD

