### **Data Monitoring**

The study will be monitored in compliance with the relevant parts of 21 CFR and according to the ICH GCP Guidelines.

A Monitor will visit the Study Center on a pre-arranged schedule to monitor adherence to the protocol and to applicable FDA regulations; and the maintenance of adequate and accurate clinical records. A Case Report Form will be completed for every subject that was enrolled to participate in the Study. The Case Report Form (CRF) will be reviewed in detail, for which the Monitor will have access to subject study records, laboratory data, and other source documentation.

Case Report Forms will be completed as information becomes available or within five days of a Study Visit.

Case Report Forms will be reviewed in detail by the Monitor who will make a decision as to their acceptability. If errors or omissions are found in the course of a data audit, or if clarification of data is required, the Case Report Form(s) in question will be corrected by the Investigator or his/her designee. Data Resolution or Query Forms may be generated on omissions or clarifications, to be completed, signed and dated, and maintained as a part of the CRF.

The Principal Investigator or a Sub-investigator will sign and date the indicated places of the Case Report Form. This signature will indicate that thorough inspection of the data therein has been made and will thereby certify the contents of the form.

The procedures outlined in the protocol and case report forms will be carefully reviewed by the Sponsor, Investigator and staff prior to Study Initiation to ensure appropriate interpretation and implementation. No deviations from the protocol shall be made except in emergency situations where alternative treatment is necessary for the protection, proper care and well being of subjects.

Amendments will be submitted to the IRB for their review and approval prior to implementation. When an amendment to a protocol substantially alters the study design or increases potential risk to the study subject, the Informed Consent form will be revised and if applicable, subject's consent to continue participation will again be obtained.

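### After an unanticipated serious adverse effect, the stopping criteria do not say whether the other subjects keep applying the gel while the event is reviewed

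*Combined protocol and SAP*

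**What the plan says.** In the combined protocol and SAP, the Stopping Criteria in section 4 contain two rules.

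The first concerns the treated site. If more than 5 patients report a local side effect worse than moderate, or if the clinician's target-lesion score is more than 50% worse than baseline in more than 5 patients, all "patients will stop medication until further review and changes made to the protocol".

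The second concerns serious events: "If any unanticipated serious adverse effects are noted all subjects will be notified and changes will be made to future protocols and submitted for approval".

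Four other places bear on the question:

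- **Serious Adverse Events:** "The Investigator will assess the case, determine the need for treatment", and consults the drug supplier. Sponsor and IRB are told "within approximately 3 working days if a serious adverse event occurs".
- **Risks of NANODOXY 1% hydrogel:** a subject with an abnormal reaction is told to call the clinic and "stop using NANODOX® until discussing symptoms with study team".
- **Data Monitoring:** "Amendments will be submitted to the IRB for their review and approval prior to implementation". Also, "No deviations from the protocol shall be made except in emergency situations where alternative treatment is necessary", for the protection of subjects.
- **Number of subjects (section 2):** 15 completers are wanted. "This may require enrolling up to 30 subjects depending on retention rates and dropouts".

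**The concern.** A stopping section exists to settle in advance what happens to subjects who are still exposed when a safety signal appears. Here it does so for local intolerance but not for serious events, which the protocol defines as including death, life-threatening events and hospitalization. The sentence on serious events specifies who is told and what may later be rewritten, and nothing about dosing in the meantime.

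This matters because of how the gel is used. Subjects apply it at home once daily from single-dose packs, with 14 +/- 2 dispensed at Visit 1 and again at Visit 2. The Study Design section allows enrolment on pre-established dates, so several subjects may be on the gel together. Safety and tolerability is the first primary outcome, and the risk section accepts that a sensitive subject could have a severe systemic reaction and that some side effects may not yet be known. After a serious event possibly caused by the gel, the other subjects would be notified, but the protocol does not say whether they should apply that night's dose.

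**Working it through.** The point is textual. The plan states no figure for serious events, so none has to be reproduced. Its one power figure, over 96% for 6 or more responses in 15 at a true 60% rate, does reproduce (exact binomial 0.966) and does not depend on this point.

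**Step 1. The two rules side by side.**

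| | Local rule | Serious-event rule |
|---|---|---|
| Trigger | severe local effect, or score more than 50% worse | unanticipated serious adverse effect |
| Patients needed | at least 6 | 1 |
| Dosing of all patients | stopped until review and protocol change | not stated |
| Enrolment | not stated | not stated |
| Other action | none stated | notify all; change future protocols |

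The severity scale is mild, moderate, severe, so worse than moderate means severe. More than 5 means at least 6 patients: 6/15 = 40% of the completers, or 6/30 = 20% of the maximum enrolment. The contrast between the two rules concerns dosing only, since neither mentions enrolment.

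**Step 2. Does another section supply the missing instruction?**

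- The advice to stop the gel and call reaches only the subject who reacts.
- The serious-event procedure covers assessment, consultation and notice. It is silent on everyone else's dosing.
- The amendment route can change this protocol, but only after IRB approval.
- The emergency exception is tied to a need for alternative treatment. It does not plainly cover pausing subjects who are well.

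None of the four sets the other subjects' dosing status.

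**Step 3. How much exposure is open.**

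- Others on the gel: between 0 and 30 - 1 = 29. The upper end needs all 30 dosing at once.
- Packs at home: up to 14 + 2 = 16 per dispensing.
- Doses before notice is due: about 3 working days is 3 calendar days, or 5 with a weekend inside. At one 15 mg pack a day that is 3 x 15 = 45 mg to 5 x 15 = 75 mg per subject. The 3 days limit notification to sponsor and IRB; they do not measure how long the question stays open, which could be shorter or longer.
- Comparator from Study Design: systemic doxycycline is used from 40 mg daily to 100 mg twice daily, so up to 2 x 100 = 200 mg a day. Five topical doses (75 mg) are less than one day at the upper level.
- Bench diffusion was 11.18 µg from 15 mg. Five doses give 5 x 11.18 = 55.9 µg, although a bench membrane is not eczematous skin.

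**Step 4. Would a pause harm the efficacy rule?** Response is counted at Visit 2 or Visit 4. Day 28 is Visit 3 and does not enter. Visit 4 is Day 42 +/- 5, wide enough for a 3-to-5-day pause, and up to 30 may be enrolled to reach 15 completers.

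**The case against.** The strongest reply is that nothing in the protocol prevents a pause. The investigator assesses each case, consults the supplier, and must contact all subjects anyway; telling them to stop could be part of that contact. The serious-event rule also fires on a single event, so leaving the response to judgement may be deliberate in a single-centre, four-week pilot treating an area the size of an index card. Expected risk is low: little drug diffused on the bench, known tetracycline allergy is excluded, and no adverse events were attributed to the gel in the earlier ulcer pilot.

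All of this stands, and it limits the urgency. It does not supply the rule. The local rule shows that the authors knew how to write an all-patient stop, and a reader of the serious-event sentence cannot tell whether its absence is intended.

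Several stronger readings are tempting, and the documents do not support them:

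- **That serious events go unmanaged, or that others must continue dosing.** Assessment, consultation and reporting are all provided for, and the text does not direct continuation.
- **That this protocol could not be changed.** The reference to future protocols may mean later versions of this one, and Data Monitoring gives an amendment route.
- **That the chance of at least one serious event measures the gap.** It can be computed for any assumed rate, but it is the chance of a first event, which no hold can prevent. The relevant quantity is further harm while the others continue, and the documents give no rate for it.
- **That enrolment must pause too.** The local rule does not pause it either.
- **That a pause would cost appreciable power.** Step 4 of the working shows why this is largely hypothetical.

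**Conclusion.** The concern holds as a gap in the rule as written. Severe local reactions or marked score worsening in 6 or more patients stop dosing for everyone; an unanticipated serious adverse effect leads to notification and later protocol changes, and no section says whether the other subjects continue during the review. This is more than a missing detail, because the weaker stated response falls on the graver event and the gel is already in subjects' homes.

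The size is modest and cannot be put as a probability. Between 0 and 29 others could be affected, each applying perhaps 3 to 5 doses if the question stayed open until notice was due. Those figures assume once-daily use and that nobody tells subjects to stop sooner. With no serious-event rate in the documents and evidence of low systemic exposure, the benefit is a safeguard against a rare second event. The protocol should be changed because the change is specific and cheap; there is no evidence that harm is likely.

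**What to change.** Reword the second rule of the Stopping Criteria along these lines:

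- A serious adverse event rated Probable or Possible on the protocol's own causality scale pauses dosing in all subjects. They are contacted and told not to use packs held at home.
- The pause lasts until the investigator and sponsor complete the causality review under Serious Adverse Events, aimed at the same period of about 3 working days.
- For an event rated Unknown, the investigator and sponsor decide on a pause at that review.
- An event rated Unlikely triggers no pause.
- Resulting changes are made to this protocol through the IRB-approved amendment route in Data Monitoring.

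Tying the rule to causality also removes the uncertainty over whether a serious allergic reaction to the gel, a risk the protocol mentions, counts as unanticipated.

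The cost is one sentence in an amendment and, if the rule is ever triggered, a short interruption of treatment, possibly for an event that proves unrelated to the gel. The effect on the 6-of-15 rule should be small, because response can still be assessed at Visit 4 within its +/- 5 days and enrolment can run to 30 to reach 15 completers.
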